4.1 Selection of Study Population

For a complete list of inclusion and exclusion criteria please refer to the study protocol.

4.2 Method of Treatment Assignment and Randomization

The following randomization criteria must be satisfied at the Baseline visit (Visit 2) in order for the patient to continue in the study and be randomized:

- 1. The patient continues to meet all inclusion and exclusion criteria, including urine and blood test results and is successfully and consistently utilizing the diary system.
- 2. Patient's FM pain satisfies the following criteria, as assessed by diary pain scores (24 hour recall):
 - a. A mean pain intensity score ≥4 and ≤9 on the 11-point (0-10) NRS scale for the 7 days immediately preceding Visit 2, and
 - b. No more than 2 individual days with a score <4 on the 7 days immediately preceding Visit 2, and
 - c. No score of 10 on any of the 7 days immediately preceding Visit 2, and

Protocol: TNX-CY-F307 Page 15 of 45

Final v1.0

d. Pain scores must be recorded on at least 5 out of the 7 days immediately preceding Visit 2.

Before the start of the study, a computer-generated randomization schedule will be prepared. Based on the randomization schedule, eligible patients will be randomly assigned in a 1:1 ratio to receive TNX-102 SL tablets or placebo tablets for 14 weeks.

Treatment A: For Days 1-14, 1 tablet of TNX-102 SL 2.8 mg taken sublingually (under

the tongue) each day at bedtime. For Days 15-98, 2 tablets of TNX-102 SL 2.8 mg (5.6 mg) taken simultaneously and sublingually each day at bedtime.

Treatment B: For Days 1-14, 1 tablet of placebo taken sublingually (under the tongue)

each day at bedtime. For Days 15-98, 2 tablets of placebo taken

simultaneously and sublingually each day at bedtime.

4.3 Treatment Blinding

This is a double-blind study. Unless otherwise specified, all study personnel are to remain blinded to study drug. Treatment assignments will not be revealed until all patients have completed the study and the database has been finalized and closed.

If AEs occur that are considered to be intolerable, the investigator must decide whether it is necessary for the patient to discontinue study drug; however, the investigator should not be unblinded unless it is imperative for the patient's overall safety to determine whether the patient received active study drug (e.g., in the event of overdose).

4.4 Minimization of Missing Data

The Sponsor believes it has incorporated strong steps into the study design to ensure minimization of missing data during the treatment period. Multiple analysis techniques to examine the impact of missing data on the robustness of results will be carried out. Additionally, with Medical Monitor approval, investigators have the option after the Week 2 visit when dose escalation has occurred, to reduce the treatment dose back to one tablet of TNX-102 SL 2.8 mg or one tablet of placebo if the higher dose is resulting in tolerability issues that would otherwise lead to study discontinuation. The importance of minimizing the amount of missing data will be discussed with all study investigators, and their awareness of the importance of patient compliance and minimal dropout rates is factored into their recruiting plans and daily patient management. In addition, investigators are advised to contact the Medical Monitor for guidance on available management options when needed to avoid patients withdrawing from the study.

4.4.1 Opioid Usage

In order to minimize confounding issues related to concomitant usage of opioids, investigators have been asked to identify candidates for this clinical trial that are not currently using chronic opioids. However, it is understood by the Sponsor that opioid usage is sometimes unavoidable for acute conditions. In the event that an opioid is required for the management of an acute pain condition, the patient will be instructed to contact the site immediately so that appropriate management decisions can be implemented and accurate medication records obtained. In addition, when feasible, study visits may be delayed to avoid the contamination of data by recent

Protocol: TNX-CY-F307 Page 16 of 45

Final v1.0

opioid usage. At a minimum, no opioid/narcotic should be utilized within 2 days of a study visit, and ideally there will be no usage during the 7 days prior to any visit.

A listing of concomitant medication CRF data identifying the use of opioids will be reviewed by the project team and approved by the Sponsor prior to database lock and unblinding, and will be used to flag records in the analysis database and in the by-patient concomitant medication listings. These flagged records will also be utilized to identify records to be censored in the sensitivity analysis described in Section 10.1.3.

4.4.2 Intermittent Missing Data

Intermittent missing daily data will not be imputed and weekly averages will be calculated using available values, even if only a single value is available for a week. Intermittent missing data (weekly averages and/or in-clinic assessments) occurring prior to discontinuing use of study drug is assumed to be missing at random, and analyses have been chosen to mitigate the impact of these missing data (Section 10.1).

5. ANALYSIS AND REPORTING

All final, planned analyses will be performed after the last patient has completed the last study visit and end-of-study assessments and all relevant study data have been processed and integrated into the analysis database. Any post-hoc, exploratory analyses completed to support planned study analyses, but which were not identified in this SAP will be documented and reported in appendices to the CSR. Any results from these unplanned analyses (post-hoc) will also be clearly identified as such in the text of the CSR.

6. SAMPLE SIZE DETERMINATION

The study is planned to enroll approximately 470 patients total in a 1:1 randomization, that is, 235 patients in each of the TNX-102 SL and placebo arms.

7. ANALYSIS POPULATIONS

The following analysis populations are planned for this study:

- All subjects: Used for summaries of dispositions of patients; tabulations of dispositions may also use the populations below.
- Safety population: all patients who took investigational product. Patients that were issued study drug, but do not return all of it will be included in the safety population. All safety analyses and demographic/baseline characterization will be performed using this population, analyzed as treated.
- Intention-To-Treat (ITT) population: all patients who were randomized. This is the primary population for efficacy analyses, and patients will be analyzed based on their randomized treatment.

Protocol: TNX-CY-F307 Page 17 of 45

Final v1.0

8. GENERAL ISSUES FOR STATISTICAL ANALYSIS

8.1 General Statistical Methodology

Descriptive summaries will be provided where appropriate for each of the primary and secondary variables. In general, tables will summarize data by treatment group and visit. All patients for a population in each treatment group will be grouped together; patients that reduce dose from two tablets per day to one tablet per day will be not be reported separately for the analyses described in this SAP, unless otherwise noted. If there are more than 10% of patients in the active arm with a dose reduction at any point in the study, summary statistics on key outcomes may be reported for patients with dose reductions.

Baseline characteristic and safety tables will be completed for the Safety Population unless otherwise specified. Efficacy tables will be presented for the ITT Population.

Continuous, quantitative variable summaries will include the number of patients (N) with non-missing values, mean, standard deviation, median, minimum, and maximum.

Categorical, qualitative variable summaries will include the frequency and percentage of patients who are in the particular category. In general, the denominator for the percentage calculation will be based upon the total number of patients in the study population for the treatment group unless otherwise specified.

Baseline values are defined as the last non-missing measurement prior to the first dose of study drug. For scores obtained via diary, baseline will be defined as the average of the scores from the 7 days prior to the baseline visit. Change from baseline will be defined as the post-baseline visit value minus the baseline value.

Study day is defined as assessment date – first dose date +1 for dates on/after first dose date and assessment date – first dose date for those before.

All analyses will be performed using SAS® Software version 9.4 or later.

8.1.1 Adjustments for Multiplicity

8.1.1.1 Multiplicity

To adjust for multiplicity and to control for overall type I error, a sequential test procedure will be applied to the primary and key secondary efficacy endpoints. If the primary analysis produces a result that is statistically significant at the two-sided 0.05 level, a significance level of 0.05 will be used for comparing the secondary endpoints in an ordered fashion. If the analysis for a secondary endpoint does not produce a statistically significant result (p-value < 0.05), then the remaining secondary endpoint analyses will automatically be considered non-significant regardless of the p-value produced.

The order of key secondary endpoints in which they are to be tested is as follows:

- Proportion of patients with a PGIC rating of "very much improved" or "much improved" at Week 14
- Change from baseline in the FIQR symptoms domain score at Week 14
- Change from baseline in the FIQR function domain score at Week 14

Protocol: TNX-CY-F307 Page 18 of 45

Final v1.0

- Change from baseline in the PROMIS score for sleep disturbance at Week 14
- Change from baseline in the PROMIS score for fatigue at Week 14
- Change from baseline to Week 14 in the weekly average of the daily diary assessment of sleep quality.

No other adjustments for multiplicity will be made and other p-values displayed in the output will be considered for descriptive summary purposes only and will not be used for formal inference. Additional details regarding statistical analysis for the listed endpoints can be found in Section 10.

8.1.2 Data Handling for Patients Who Withdraw/Drop Out from the Study

Patients who withdraw/drop out from the study will have the early termination (ET) data collected at their ET visit included in the analysis at the closest visit (Week 2, 6, 10, 14), using midpoints between visits to window the early termination. If this results in two records for a given visit, then the one closest to the targeted date will be used. Visits beyond day 112 (two weeks past the target day for Week 14) will not be mapped and reported with Week 14; they may appear in the last observation analyses (see below).

For example, a patient with a non-missing Week 10 clinic assessment collected on Day 72 that has early termination data collected on Day 79, would have the early termination data mapped to Week 10; however, since Day 72 data is present and closer to the target date, it would be analyzed and the Day 79 data would be excluded. A patient with missing Week 10 data who early terminates on Day 79 would have the Day 79 data analyzed with the Week 10 data.

Patients who provide 14 weeks of diary pain data will be analyzed as completers for purposes of the primary analysis, even if for some reason they are unable to attend a Week 14 final study visit. As a specific example, a patient who successfully provides 14 weeks of diary data as described in Section 8.2.1, but who is unable to attend a final study visit during the required time window because of travel or other circumstances, would be analyzed as a completer for purposes of the primary endpoint, but would be missing non-diary based secondary outcome measures at the Week 14 endpoint.

For safety data, the last observation available will be summarized in addition to the presentation above (grouping ET visits with the closest planned visit); this will combine the ET visit data with the completers' Week 14 data, regardless of when the ET occurred.

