13.4.4. Secondary Efficacy Analyses

Secondary efficacy analyses will be based on the ITT population only. For PGIC, patients with a "very much improved" or "much improved" response at the Week 14 endpoint will be considered responders. Patients with results in any other category or who discontinue early will be considered non-responders. A categorical analysis of PGIC responder status (yes/no) will compare the treatment arms with a difference in proportions Z test (equivalent to a Pearson's Chi Squared). The percentages of responders and the 95% CIs of the percentages as well as the difference in the percentages and its 95% CI will be reported.

Analysis of continuous secondary endpoints and adjustments for missing data will be described in detail in the SAP. Significance tests of treatment differences will be tested at the two-sided 0.05 level and corresponding 95% confidence intervals will be calculated.

To adjust for multiplicity and to control for overall type I error, a sequential test procedure will be applied to the efficacy endpoints. If the primary analysis produces a result that is statistically significant at the 0.05 level, a significance level of 0.05 will be used for comparing the secondary endpoints in an ordered fashion. If the analysis for a secondary endpoint does not produce a statistically significant result at the 0.05 level, then the remaining secondary endpoint analyses

will automatically be considered non-significant regardless of the p-value produced. The order in which the secondary endpoints are to be tested will be specified in the SAP.

No other adjustments for multiplicity will be made and other p-values displayed in the output will be considered for descriptive summary purposes only and will not be used for formal inference. Full details regarding the statistical analyses for the listed endpoints, including graphical presentations, can be found in the SAP.

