8.1.4 Imputation of Missing Data

For individual daily pain scores, since a mean is used in the calculation of the primary endpoint, it is not necessary to replace values missing on random intermittent days; weeks will have average values as long as a single value for that week is present.

Daily sleep diary data will be handled in an identical manner to the pain scores.

Continuous outcomes included in the list of key secondary outcomes that are collected in-clinic will be handled as above, minus the step of creating weekly averages of daily values and with steps being done by visit instead of week.

Patients with missing PGIC at a given visit will be considered non-responders at that visit for the purposes of treatment comparisons and efficacy claims; additional tabulations will summarize the number and percentage in each category out of non-missing values as well as a count of the missing values.

No missing safety data will be imputed.

Protocol: TNX-CY-F307 Page 20 of 45

Final v1.0

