8.2.3 Patient Global Impression of Change (PGIC)

PGIC is a question completed by the patient at Weeks 2, 6, 10, and 14. The patient will rate the change in their overall fibromyalgia symptoms on a 1-7 Likert scale, where 1 is "Very Much Improved" and 2 is "Much Improved". Scores of 1 and 2 will be considered PGIC responders, and all other scores will be considered non-responders for that visit. The proportion of responders in each treatment arm will be analyzed. Any missing PGIC score will be considered a non-responder for that visit.

Protocol: TNX-CY-F307 Page 22 of 45

Final v1.0

An exploratory analysis will include "Minimally Improved" (3) as responders, in addition to scores of 1 and 2.

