10.2 Secondary Efficacy Analyses

Secondary efficacy analyses will be based on the ITT population only.

Continuous Endpoints

For the purposes of possible label claims and reported p-values entered into the multiplicity algorithm, an approach identical to the primary analysis will be used for all continuous outcomes. See Section 8.1.4 for the imputation algorithm and Section 10.1.2 for the analysis approach.

Outcomes using these analyses will include:

- Change from baseline in the FIQR symptoms domain score
- Change from baseline in the FIQR function domain score
- Change from baseline in the PROMIS score for sleep disturbance
- Change from baseline in the PROMIS score for fatigue
- Change from baseline in the weekly average of the daily diary assessment of sleep quality.

For each, all time points will be summarized, but the primary time point of interest is Week 14. Time points other than Week 14 are considered exploratory. The estimand for each is identical to the primary, substituting for the endpoint in question.

For the sleep quality assessment collected via a daily patient diary, the baseline score and the weekly scores for each patient will be calculated as the weekly average score based on the mean of the scores recorded for that study week (Section 8.2.2).

In addition to the above analyses using the primary imputation and model, analyses will be repeated on the outcomes above, but using observed data only without imputation.

Categorical Endpoints

A categorical analysis of PGIC will compare the treatment arms with a difference in proportions Z test (equivalent to a Pearson's Chi Squared). Patients with results of "very much improved" or "much improved" (defined as responders) will be compared to all other categories (defined as non-responders). Patients with missing data will be considered non-responders. The percentages of responders and the 95% CIs of the percentages as well as the difference in the percentages and its 95% CI will be reported. A summary of frequency counts for all PGIC responses for each time point will be presented; Week 14 is of primary interest and all other time points are considered exploratory.

Protocol: TNX-CY-F307 Page 28 of 45

Final v1.0

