15.3 Appendix C

The following conventions will be used for calculation of a patient's nominal Week 14 score. All other week scores are calculated relative to the nominal Week 14 interval.

Landmark Endpoint Visit Day	Last Available Diary Score Recorded	Days Used to Calculate "Week 14"	Comment
99	98	92-98	Ideal condition with final study visit on Day 99, last diary data will be day 98.
100	99	93-99	
101	100	94-100	
102	101	95-101	
103	102	96-102	
104	103	97-103	
105	104	98-104	
106	105	99-105	
Out of window (late)	106+	99-105	Since the Week 14 endpoint is Day 99 -4/+7 days, days after 106 are outside the Week 14 nominal interval. Any scores recorded after day 106 will be ignored.
98	97	91-97	
97	96	90-96	
96	95	89-95	
95	94	88-94	
94	93	87-93	Out of window, but allowed
93	92	85-92	Out of window, but allowed
92	91	85-91	Out of window, but allowed
<92	<91	85+	Must have a valid score occurring on/after day 85 or will be missing for week 14

Final v1.0

Page 42 of 45 Protocol: TNX-CY-F307

Protocol: TNX-CY-F307 Page 43 of 45

Final v1.0

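### For Week 14 PGIC, the protocol counts every early discontinuer as a non-responder, but the SAP lets a late early-termination rating of 1 or 2 count as a response and does not declare the change

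*SAP*

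**What the plan says.** **Protocol.** Section 13.4.4 defines Week 14 PGIC responders as the two best ratings (1 and 2) and then states: "Patients with results in any other category or who discontinue early will be considered non-responders". Early discontinuation and a poor rating are joined by *or*, so discontinuation alone is enough, whatever the rating.

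**SAP responder rule.** It appears in three places, and none of them mentions discontinuation:
- 8.1.4: "Patients with missing PGIC at a given visit will be considered non-responders at that visit".
- 8.2.3: ratings 1 and 2 are responses and all other ratings are not; "Any missing PGIC score will be considered a non-responder for that visit".
- 10.2: the same split of ratings; "Patients with missing data will be considered non-responders".

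**SAP visit mapping.** Section 8.1.2 has the "early termination (ET) data collected at their ET visit included in the analysis at the closest visit (Week 2, 6, 10, 14", with the boundaries at the midpoints between visits. The upper limit is: "Visits beyond day 112 (two weeks past the target day for Week 14) will not be mapped and reported with Week 14". PGIC is not exempted. Protocol 11.5.2 lists PGIC among the assessments at the ET visit, so there is a rating to map.

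**Declared changes.** SAP Section 13 lists one item only, the added analysis of PGIC as a continuous score.

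**The concern.** One patient can receive two different outcomes. Someone who stops early, attends an ET visit on Day 88 and rates 2 has an observed Week 14 rating under the SAP and is a responder. Under the protocol the same patient is a non-responder because of the early stop.

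PGIC is the first of six key secondary endpoints tested in a fixed order. If it misses 0.05, the "remaining secondary endpoint analyses will automatically be considered non-significant regardless of the p-value produced" (SAP 8.1.1.1). An endpoint in that position should not have two defensible responder counts once treatment codes are known, and a departure from an explicit protocol rule should be on record.

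**Working it through.** **1. The SAP's own mapping example.** Protocol Table 2 sets Week 10 at Day 71 and Week 14 at Day 99. The SAP example sends a Day 79 ET visit to Week 10. Distances: |79 − 71| = 8 and |79 − 99| = 20, so Week 10 is nearer. The example also prefers Day 72 to Day 79: 1 day from target against 8. Both statements are reproduced.

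**2. Where Week 14 begins.** The midpoint is (71 + 99)/2 = Day 85. The SAP's description of Day 112 as two weeks past target implies a target of Day 98 (98 + 14 = 112, whereas 99 + 14 = 113). With targets 70 and 98 the midpoint is Day 84. ET visits after Day 84 or 85, up to Day 112, therefore map to Week 14. The one-day ambiguity does not affect the point.

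**3. The two rules side by side, for early discontinuers**

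| Case | Protocol 13.4.4 | SAP |
|---|---|---|
| ET visit mapped to Week 2, 6 or 10 | Non-responder | Non-responder (Week 14 missing) |
| No ET visit | Non-responder | Non-responder (missing) |
| ET visit mapped to Week 14, rating 3–7 | Non-responder | Non-responder |
| ET visit mapped to Week 14, rating 1–2 | Non-responder | **Responder** |

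Only the last row differs. For these patients the SAP rule can only add responders, in either arm.

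**4. How many.** The documents give 235 patients per arm but no dropout, ET-attendance or PGIC rates, so the rates here are assumptions: dropout 10–30% spread evenly over 98 days, ET attendance 50–100%, and 10–40% of attenders rating 1 or 2 (middle case 20%, 75%, 25%).

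Affected per arm = 235 × dropout × (days/98) × attendance × share rating 1–2.

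Mapping goes by the day of the ET visit, and Protocol 11.5.2 encourages the visit even after a lapse in study drug, so the lag matters:
- No lag: discontinuations on Days 85–98, 14/98 = 0.143. Low 235 × 0.10 × 0.143 × 0.50 × 0.10 = 0.17; middle 1.26; high 235 × 0.30 × 0.143 × 1.00 × 0.40 = 4.03.
- Assumed 14-day lag: discontinuations on Days 71–98 have ET visits on Days 85–112, 28/98 = 0.286. Low 0.34; middle 2.52; high 8.06.

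**5. Effect on the test.** Only the net difference between arms matters much. One net patient is 1/235 = 0.43 percentage points. With SE = √(2p(1 − p)/235), the SE is 3.99, 4.23 and 4.40 points at p = 25%, 30% and 35%, so z moves by 0.107, 0.101 and 0.097.

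Hypothetical counts out of 235 per arm, pooled two-proportion Z test (the SAP's test):

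| Counts | z | p |
|---|---|---|
| 80 v 60 | 2.017 | 0.0437 |
| 79 v 59 (one fewer in each arm) | 2.026 | 0.0428 |
| 79 v 60 (one net patient) | 1.920 | 0.0548 |
| 85 v 60 | 2.497 | 0.0125 |
| 83 v 60 (two net patients) | 2.306 | 0.0211 |

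Equal reclassification barely moves the result. One net patient crosses 0.05 only from a borderline start. From 85 v 60 it takes a net loss of six on one arm (85 − 79 = 6) to pass 0.05.

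**The case against.** **The protocol defers to the SAP.** Protocol Section 13 promises a complete description of the analyses there, and 13.4.4 itself ends by sending the reader to it for full details. The visible SAP is consistent: map by midpoint, count 1–2 as response, count missing as failure. This stands to the extent that the SAP is the document of detail, and declaring the mapping would be an acceptable cure. It does not cancel a responder rule that the protocol states outright. The specific deferral in 13.4.4 on missing data concerns continuous endpoints, and an observed ET rating is not missing.

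**Uniform handling.** The SAP treats ET data alike for all in-clinic endpoints, whereas the protocol rule makes a late discontinuer observed for FIQR and PROMIS but failed for PGIC. That is a fair argument for the alternative fix, though not for leaving the difference undeclared.

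**Unseen text.** The imputation steps that SAP 8.1.4 refers to are not visible. Its PGIC sentence is, and it agrees with 8.2.3 and 10.2.

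**Stronger readings that the documents do not support:**
- A reader might infer from Appendix C, which marks landmark visits on Days 92–94 "Out of window, but allowed", that earlier visits are certain early discontinuations by the calendar alone. Appendix C governs the diary week, and its row for visits before Day 92 still yields a Week 14 value if there is a diary score from Day 85 on. It draws no line for PGIC or for completer status.
- A reader might infer that a disposition rule also settles how to treat completers seen late. It does not. SAP 8.1.2 treats a patient who cannot attend the final visit within the window as missing the non-diary measures, and that question is separate.
- A reader might infer type I error inflation or concealment. Neither follows: the direction is unknown, and the silence of Section 13 is an omission.

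**Conclusion.** The conflict is real and narrow. For early discontinuers with an ET visit mapped to Week 14 and a rating of 1 or 2, the two documents give opposite outcomes on the first gated secondary endpoint, and the SAP does not say so. For all other early discontinuers they agree.

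The number affected is probably small. The range of under 1 to about 8 per arm rests on the assumed dropout, attendance and rating shares and on the lag to the ET visit; it is an illustration and not a bound. The effect depends on the imbalance between arms, which cannot be predicted. In practice the sequence would change only if the PGIC p-value were already near 0.05. The point should be fixed because the endpoint gates five others and the correction is nearly free.

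**What to change.** Before unblinding, do one of the following.

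**Preferred.** In SAP 8.1.4, 8.2.3 and 10.2, add early discontinuation to the Week 14 PGIC non-responder rule, as in Protocol 13.4.4. Identify early discontinuation from the disposition record. State that this overrides the 8.1.2 mapping for the Week 14 PGIC responder endpoint, and report the mapped-ET rule as a sensitivity analysis.

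**Alternative.** Keep the mapping, declare it in SAP Section 13 as a change from the protocol, and report the protocol rule as a sensitivity analysis.

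**Cost.** The preferred fix needs one sentence in three places, the override statement, a disposition flag in the derivation and one extra run of a simple test. The responder rate may be marginally lower in either arm, and a late discontinuer will count as observed at Week 14 for FIQR and PROMIS but as a PGIC non-responder. The protocol rule already implies that asymmetry.
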